#### TABLE 1: SCHEDULE OF TREATMENTS AND TESTS:

Renal VT Version 1.3 November 2012

# 5. Endpoints:

# **5.1: Primary Endpoint:**

The following primary endpoint will be assessed: Time to first event requiring appropriate ICD therapy or Incessant VT (VT occurring below the ICD rate cut-off); this will be assessed in the on-treatment patient cohort.

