Control Group:	Subjects in the control group will undergo a standard procedure for catheter-based VT ablation.				
Primary Endpoint:	
 
Time to first event requiring appropriate ICD therapy for ventricular arrhythmia or Incessant VT (VT occurring below the ICD rate cut-off)
 
				
Secondary Endpoints:	
 
Appropriate ICD therapy for ventricular arrhythmia
 
Appropriate ICD Shocks ventricular arrhythmia
 
Inappropriate ICD therapy
 
All ICD therapy (Appropriate + Inappropriate)
 
A composite of Mortality, ICD storm, and Incessant VT (VT occurring below the ICD rate cut-off)
 
Number of Hospitalizations for Cardiovascular Causes.
 
Total VT burden (Number of episodes).
 
All-Cause Mortality.
 
The occurrence of ICD storm, defined as ≥3 appropriate shock therapies within 24 hours.
 
Differences in blood hormone measurements (including norepinephrine, aldosterone, renin, and BNP).
 
Differences in Cardiac parameters, including LV size (septal and free wall thickness) and mitral inflow (E&A velocity), as measured by trans-thoracic echocardiography.
 
Procedure related adverse events including, but not limited to hematomas, pseudoanuerysms, renal artery stenosis, renal impairment, thromboembolic events, stroke, pericardial bleeding including tamponade and myocardial infarction
 
Change in blood pressure
 
				

	
 
15. Development of orthostatic hypotension
 
16. Other individual complication rates including, but not limited to MI and death.
 
17. 30-day Major Complication Rate defined as death, stroke, MI or any other serious adverse events related to the treatment or procedure within the first 30 days or through hospital discharge (whichever is longer);
 
18. Procedure time
 

Primary Analytical Analysis:	Intent to treat analysis
Secondary Analytical Analysis:	Per protocol analysis
Principal Investigator:	[name]. Mount Sinai School of Medicine [name]
Site, Monitoring, and Data Management Center	Electrophysiology Clinical Research Group Mount Sinai School of Medicine [name]
Data Safety and Monitoring Board:	TBD

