# 5.2: Secondary Endpoints:

The following secondary endpoints will be assessed:

- 1) Appropriate ICD therapy for ventricular arrhythmia assessed in the full intention-to-treat patient cohort
- 2) Appropriate ICD Shocks for ventricular arrhythmia
- 3) Inappropriate ICD therapy
- 4) All ICD therapy (Appropriate + Inappropriate)
- 5) A composite of Mortality, ICD storm, and Incessant VT (VT occurring below the ICD rate cut-off)
- 6) Number of Hospitalizations for Cardiovascular Causes.
- 7) Total VT burden (Number of episodes).
- 8) All-Cause Mortality.
- 9) The occurrence of ICD storm, defined as  $\geq 3$  appropriate shock therapies within 24 hours.
- 10) Differences in blood hormone measurements (including norepinephrine, aldosterone, renin, and BNP).
- 11) Differences in BUN/creatinine measurements.
- 12) Differences in cardiac parameters, including LV size (septal and free wall thickness) and mitral inflow (E&A velocity), as measured by trans-thoracic echocardiography.
- 13) Procedure related adverse events including, but not limited to hematomas, pseudoanuerysms, renal artery stenosis, renal impairment, thromboembolic events, stroke, pericardial bleeding including tamponade and myocardial infarction.
- 14) Development of orthostatic hypotension
- 15) Changes in blood pressure
- 16) Other individual complication rates including, but not limited to MI and death.
- 17) 30-day Major Complication Rate defined as death, stroke, MI or any other serious adverse events related to the treatment or procedure within the first 30 days or through hospital discharge (whichever is longer);
- 18) Procedure time

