# 7. Sample Size Calculation:

We generated our sample size using the following key assumptions:

- 1. In patients receiving catheter ablation for VT alone, the estimated success rate (absence of ICD therapy) at 2 years is 65%
- 2. In patients receiving RSDN in addition to VT ablation, we expect a 30% improvement such that the estimated 2 year success rate is 85%

The power analysis revealed that a 30% improvement in therapy with RSDN would be detected with 83 patients per arm (80% power, 2-sided alpha error of 0.05). This would require an enrollment of a total of 168 patients, with follow-up of 2 years. We expect an ~10% loss to follow-up. Accordingly, we will plan to enroll an additional ~10% of patients so as to have sufficient number of randomized patients: this would require 184 patients. In addition, we expect 10% of patients will have renal vasculature inappropriate for the RSDN procedure (these are patients that will be consented pre-procedure, but will screen out after renal angiography during the VT ablation procedure). Accordingly, we will ultimately plan to include a total of 202 patients: ~18 patients would screen out after renal angiography, and there would remain a total of 92 patients randomized to each arm.

This study is divided into two phases: a PILOT phase (to include 20 patients) followed by the remaining 182 patients to a total of 202 patients. The PILOT phase will be conducted at 2 sites: Homolka Hospital (Prague, Czech Republic) and Mount Sinai Medical Center. An interim safety

[figure not shown]
analysis for the primary endpoint will be conducted when all patients in the PILOT phase (20 subjects) have completed the 1-month follow up visit.

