### 9. Pre-Procedure and Ablation Study Design Flow-Chart

#### **PRE- AND ABLATION PROCEDURE**

### 9.1.1 **PRE-PROCEDURE**

The following tests and procedures will occur before the ablation:

- Recording of patient medical history (including details of VT both clinical/ICD)
- Recording medication history (including all AAD ever used, duration of use)
- Obtain β-HCG in females of child bearing age the morning of the procedure as per usual clinical practice
- Baseline assessment of arrhythmia burden and type: Office/inpatient records, ICD interrogation report
- Baseline NIH stroke scale
- If performed for any reason, collect any pre-procedural imaging: MRI/CT and Renal Ultrasounds within 6 months of procedure
- Baseline laboratory, including complete blood count, standard electrolyte panel, renal function, and brain natriuretic peptide levels.
- Baseline Transthoracic Echocardiogram
- Baseline blood pressure. Proper blood pressure measurement technique is essential: i) patient should sit quietly in a chair with his/her back supported for 5 minutes before taking the measurement; ii) use of the correct cuff size with the air bladder encircling at least 80% of the arm (the adult large cuff for the majority of patients); iii) support the arm at heart level during the cuff measurement; iv) a minimum of 2 readings should be taken at intervals of at least 1 minute and the average of those readings should be taken to represent the patient's blood pressure; v) the blood pressure should be measured
- Consent must be obtained before the VT ablation procedure.
- Randomization into one of two groups will be performed by opening the Randomization envelope after Renal Angiography.

Study/Experimental Group: These subjects will undergo catheter-based sympathetic renal denervation.

Placebo Control Group: These subjects will receive no further intervention..

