#### 9.1.4 RENAL SYMPATHETIC ABLATION PROCEDURAL DETAILS

• In patients randomized to receive RSDN, the procedure will be performed after the VT ablation on therapeutic anticoagulation with intravenous heparin.

- Abdominal aortography will be performed to assess the renal arteries for the suitability of catheter-based renal denervation in all patients. For those patients in whom the angiogram demonstrates that the renal anatomy is inappropriate for the RSDN procedure (small renal arteries, extensive atherosclerosis, renal stenosis, etc), the patient will be excluded from the study as a screen failure. The patient's baseline information will be collected but no further follow-up required (beyond assessing for any adverse events related to the procedure). If the renal arteries are deemed suitable for RSDN, the patient will then undergo randomization.
- Randomization will be done by permuted-block randomization centrally and will be stratified by site. Allocation concealment shall be maintained at all sites by the use of a web-based central randomization scheme. The operating physician controlling the delivery of ablative energy will be aware of the outcome. This approach has been selected to minimize (1) study bias and (2) placebo effect. The randomization schema will be blocked by size for each site.
- After confirmation of eligibility, an irrigated radiofrequency ablation catheter will be introduced sequentially into each renal artery.
- The ablation catheter is placed within a long vascular sheath and advanced into the renal artery. The sheath is advanced over the catheter to engage the renal artery ostium and allow for contrast injection and visualization of the vessel during catheter manipulation.
- After completion of the measurement, no more than six radiofrequency ablation lesions separated both longitudinally and rotationally (a —spid pattern", see figure) will be placed per renal artery. The power will be started at 10 W and titrated to a maximum 20 W, as deemed appropriate by the impedance drop (goal 10% drop). Each lesion should be between 30-120 seconds in duration (no more than 120 seconds per lesion).

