#### **10.4 Withdrawal of Subjects**

A subject may withdraw from the study at any time should they choose to do so. Additionally, subjects may be withdrawn by the investigator if deemed appropriate due to safety or compliance issues.

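### The primary endpoint is assigned to an undefined on-treatment cohort in Section 5.1, against the intention-to-treat primary analysis in the Protocol Summary

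*Combined protocol and SAP*

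**What the plan says.** The Protocol Summary and Section 5.1 give the same primary composite; Section 5.1 words it as "Time to first event requiring appropriate ICD therapy or Incessant VT (VT occurring below the ICD rate cut-off"). They differ on who is analysed:

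- **Protocol Summary, Primary Analytical Analysis:** "Intent to treat analysis". Per-protocol is listed as the secondary analysis.
- **Section 5.1:** "this will be assessed in the on-treatment patient cohort".
- **Section 5.2, item 1 (a secondary endpoint):** "Appropriate ICD therapy for ventricular arrhythmia assessed in the full intention-to-treat patient cohort".

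The on-treatment term occurs only in Section 5.1. No section defines it, relates it to per-protocol, or says how incomplete RSDN, crossover or withdrawal is classified. Section 7 names no analysis set for the primary comparison.

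Three other places bear on who could be excluded. On suitability for the procedure, Section 9.1.4 says: "If the renal arteries are deemed suitable for RSDN, the patient will then undergo randomization". Of the control group, Section 9.1.1 says: "These subjects will receive no further intervention". Section 10.4 adds that "subjects may be withdrawn by the investigator if deemed appropriate due to safety or compliance issues".

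**The concern.** The two statements of the primary population cannot both govern. Section 5.1 is also hard to dismiss as a slip. Read with item 1 of Section 5.2, it looks like a deliberate ranking, with on-treatment primary and intention-to-treat secondary, which reverses the summary.

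The design makes this matter. Non-receipt of the extra procedure can arise only in the RSDN arm, and Section 9.1.4 says the operator delivering the energy knows the allocation. Exclusion could therefore follow from decisions made after allocation is known, which is what intention-to-treat protects against. If the excluded RSDN patients have a worse prognosis than average, the comparison is biased toward RSDN; if better, against it. There is no bias if their prognosis is average, or if equal shares with the same prognosis leave both arms. The protocol gives no basis for knowing which applies. Two competing primary populations also permit a choice once results are known.

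**Working it through.** **1. Does Section 5 contain an intention-to-treat analysis of the primary composite?**

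| Place | Outcome | Population |
|---|---|---|
| Protocol Summary | Time to first appropriate ICD therapy or incessant VT | Intention-to-treat (per-protocol secondary) |
| Section 5.1 | Same composite | On-treatment, undefined |
| Section 5.2, item 1 | Appropriate ICD therapy only | Intention-to-treat |
| Section 5.2, other items | Various | None stated |

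Item 1 drops incessant VT and the time-to-first-event wording, so it is a different endpoint. Within Section 5 the answer is no; only the summary implies such an analysis.

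**2. Who could separate the two cohorts?** Patients with unsuitable renal anatomy leave before randomisation (Section 9.1.4), so they do not. What remains is RSDN not delivered or not completed after randomisation, crossover, and withdrawal, which can occur in either arm. The documents give no rate for any of these. They also do not say whether randomisation comes before or after VT ablation is finished.

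**3. Illustration of bias with no true effect.** From Section 7: 92 randomised per arm, and a control event rate of 1 − 0.65 = 35%, applied here to both arms. Assumed: a share q of the RSDN arm is excluded, with event rate r. The rate among the RSDN patients who remain is

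(0.35 − q·r) / (1 − q).

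For q = 10% and r = 60%: (0.35 − 0.06) / 0.90 = 32.2%, which is 2.8 points below 35%. The false-benefit rate is the probability of a significant result in favour of RSDN. It comes from exact enumeration of a pooled two-proportion z-test, uncorrected, two-sided 0.05.

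| RSDN excluded | Event rate in excluded | Controls excluded | Spurious benefit (points) | False-benefit rate |
|---|---|---|---|---|
| 0% | – | 0% | 0 | 2.6% |
| 1% | 60% | 0% | 0.3 | 2.7% |
| 2% | 60% | 0% | 0.5 | 2.9% |
| 5% | 60% | 0% | 1.3 | 3.8% |
| 10% | 35% | 0% | 0 | 2.5% |
| 10% | 60% | 0% | 2.8 | 5.8% |
| 10% | 20% | 0% | −1.7 | 1.4% |
| 15% | 80% | 0% | 7.9 | 19.8% |
| 15% | 20% | 0% | −2.6 | 1.0% |
| 10% | 60% | 5%, same event rate | 1.5 | 3.9% |
| 10% | 60% | 10%, same event rate | 0 | 2.5% |

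The outcome is treated as binary at 2 years although the endpoint is time to first event, so these figures only illustrate.

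**4. What intention-to-treat costs in power.** Section 7 says its target difference (65% against 85% success) "would be detected with 83 patients per arm (80% power, 2-sided alpha error of 0.05"). The continuity-corrected two-proportion formula gives exactly 83 per arm; without the correction it gives 73.

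Now let a share f of the RSDN arm go untreated and have the control success rate. RSDN-arm success under intention-to-treat is 0.85(1 − f) + 0.65f. With d the difference in success rates, p̄ their mean and n = 83, corrected power is

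Φ{ [ (d − 1/n)√n − 1.96·√(2p̄(1 − p̄)) ] / √(p₁(1 − p₁) + p₂(1 − p₂)) }.

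At f = 0: (0.188 × 9.110 − 1.200) / 0.596 = 0.86, so power is 80.5%. Uncorrected power replaces d − 1/n with d.

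| f | RSDN-arm success | Power, corrected | Power, uncorrected | n per arm for 80%, corrected |
|---|---|---|---|---|
| 0% | 85% | 80.5% | 85.2% | 83 |
| 5% | 84% | 75.4% | 80.8% | 92 |
| 10% | 83% | 69.8% | 75.8% | 103 |
| 15% | 82% | 63.8% | 70.2% | 117 |

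**The case against.** The strongest reply is that the two cohorts may hardly differ. Anatomical failures are removed before randomisation. Table 1 in Section 4 places angiography, randomisation and RSDN in the same procedure visit. RSDN is a single procedure, so later withdrawal need not make a patient untreated. With 1% or 2% excluded at a 60% event rate, the false-benefit rate is 2.7% or 2.9% against 2.6% with none. The 19.8% extreme needs 15% of one arm excluded, an 80% event rate among them and no control exclusions, and no figure in the documents supports any of these. This stands as a limit on the size, not as an answer to the contradiction.

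A second reply is that an undefined term cannot be shown to remove mainly RSDN patients. It might mean analysis by treatment received, or require a completed VT ablation, which both arms undergo. That is fair, and the direction is therefore stated as a possibility. It does not rescue Section 5.1, because analysing by treatment received also departs from the randomised comparison.

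A third is that the power cost depends on the test. Without the continuity correction, 80% is still met when 5% go untreated (80.8%) and is missed at 10% (75.8%). This also stands, so both versions are shown.

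**Conclusion.** The point holds and should be fixed before the primary analysis. The population that decides the trial is stated in two incompatible ways, one of them undefined, and Section 5 offers no intention-to-treat analysis of the composite. That conclusion comes from the text alone and needs no assumption.

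The size of the consequence cannot be fixed from the documents. With 5% to 15% of the RSDN arm excluded, event rates of 20% to 80% among them and no control exclusions, the distortion runs from 2.6 points against RSDN to 7.9 points in its favour, and the false-benefit rate from 1.0% to 19.8%. It shrinks toward nothing if exclusions are rare, balanced with the same prognosis, or of average prognosis.

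**What to change.** Two changes follow directly from the contradiction:

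1. In Section 5.1, replace the final clause so that the composite is assessed in all randomised patients, analysed in the arm assigned (intention-to-treat), matching the Protocol Summary.
2. Define one on-treatment or per-protocol cohort: what counts as treated in each arm, and how incomplete RSDN, crossover and withdrawal are handled. Use it for a supportive analysis of the same composite.

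Two more are advisable:

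3. In Section 5.2, state intention-to-treat as the default for the secondary efficacy endpoints, instead of attaching it to item 1 alone.
4. In Section 7, state the share of randomised RSDN patients assumed to go untreated and check power under intention-to-treat. The present allowances cover loss to follow-up and screen failure before randomisation, but not this.

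The text cost is a short amendment to Sections 5.1, 5.2 and 7, with no new data. The statistical cost is the power loss shown above. If 5%, 10% or 15% go untreated, holding 80% with the continuity correction would take 92, 103 or 117 evaluable patients per arm instead of 83, before loss to follow-up.

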# 5.2: Secondary Endpoints:

The following secondary endpoints will be assessed:

- 1) Appropriate ICD therapy for ventricular arrhythmia assessed in the full intention-to-treat patient cohort
- 2) Appropriate ICD Shocks for ventricular arrhythmia
- 3) Inappropriate ICD therapy
- 4) All ICD therapy (Appropriate + Inappropriate)
- 5) A composite of Mortality, ICD storm, and Incessant VT (VT occurring below the ICD rate cut-off)
- 6) Number of Hospitalizations for Cardiovascular Causes.
- 7) Total VT burden (Number of episodes).
- 8) All-Cause Mortality.
- 9) The occurrence of ICD storm, defined as  $\geq 3$  appropriate shock therapies within 24 hours.
- 10) Differences in blood hormone measurements (including norepinephrine, aldosterone, renin, and BNP).
- 11) Differences in BUN/creatinine measurements.
- 12) Differences in cardiac parameters, including LV size (septal and free wall thickness) and mitral inflow (E&A velocity), as measured by trans-thoracic echocardiography.
- 13) Procedure related adverse events including, but not limited to hematomas, pseudoanuerysms, renal artery stenosis, renal impairment, thromboembolic events, stroke, pericardial bleeding including tamponade and myocardial infarction.
- 14) Development of orthostatic hypotension
- 15) Changes in blood pressure
- 16) Other individual complication rates including, but not limited to MI and death.
- 17) 30-day Major Complication Rate defined as death, stroke, MI or any other serious adverse events related to the treatment or procedure within the first 30 days or through hospital discharge (whichever is longer);
- 18) Procedure time

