#### **Device Specific Detection Parameters**

#### 9.2 SAFETY

We anticipate no significant increase in adverse events as compared to the VT ablation or renal angiography procedure. The local site primary investigator will oversee the safety of the study at his/her site. All adverse events will be reported to the Data Coordinating Center (Mount Sinai School of Medicine). Adverse events will be monitored and tallied for each 50 patients enrolled in the study (after the 20 patients enrolled during the PILOT phase), and presented to an independent Cardiologist (who will serve as the Data Safety Monitoring individual). All adverse events will be adjudicated as being either: 1) related to the renal denervation procedure; 2) related to the VT ablation procedure or 3) unrelated to either procedure. Because of the small size of this study, the DSMB will consist of one Cardiologist; the PI will also be present at the meetings to relate any pertinent trial information. However, recommendations are solely up to the discretion of the DSMB

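### Safety item 13 and the other-serious-event part of item 17 count only events judged related, under an attribution scheme that could treat the same late renal finding differently in the two arms

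*Combined protocol and SAP*

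**What the plan says.** Two of the secondary endpoints in section 5.2 depend on a relatedness judgement.

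- Item 13: "Procedure related adverse events including, but not limited to hematomas, pseudoanuerysms, renal artery stenosis, renal impairment, thromboembolic events", followed by stroke, pericardial bleeding with tamponade, and myocardial infarction. It is the only endpoint that names renal artery stenosis or renal impairment.
- Item 17, the 30-day major complication rate: "death, stroke, MI or any other serious adverse events related to the treatment or procedure within the first 30 days", extended to hospital discharge if that is later. The relatedness wording clearly governs the other serious events. Whether it also governs death, stroke and MI is ambiguous.

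The safety section (headed 9.2) gives the only attribution scheme: "All adverse events will be adjudicated as being either: 1) related to the renal denervation procedure", with VT-ablation-related and unrelated as the other two options. It gives no criteria, does not say who makes the call, and does not say whether that person is masked.

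Four other places bear on this:

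- The Protocol Summary calls the trial single-blinded and states blinding only for the patient.
- Section 9.1.4 says of the operator: "The operating physician controlling the delivery of ablative energy will be aware of the outcome". It also has aortography done in every patient before randomisation.
- Section 9.3.2 limits the independent events committee to ICD events.
- Section 9.1.1 gives controls no intervention beyond VT ablation and the angiography.

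Several endpoints carry no relatedness condition: item 8 ("All-Cause Mortality"), item 11 ("Differences in BUN/creatinine measurements"), items 14 and 15 on orthostatic hypotension and blood pressure, and item 16 ("Other individual complication rates including, but not limited to MI and death").

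**The concern.** A randomised safety comparison is fair when both arms are counted by one rule. Here the rule for item 13, and for part of item 17, includes a causal judgement whose options differ by arm. For an RSDN patient with a narrowed renal artery at 6 months, an obvious category is available. For a control with the same finding, that category does not exist. The remaining choices are the VT ablation, which does not readily explain a late renal artery finding, or unrelated, which removes the event from the endpoint. Events caused by the aortography have no category in either arm.

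The rationale section says the trial will evaluate the safety of adjunctive RSDN. Renal artery and renal function events are among the harms most specific to that procedure, and item 13 is the only endpoint that names them as events. If the filter works differently by arm, an excess in the RSDN arm could reflect attribution and not harm.

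**Working it through.** **The plan's own figures.** The plan gives no event rate, hypothesis test or power for any safety endpoint. Its only calculation is for efficacy in section 7: 65% against 85% success, 80% power, two-sided alpha 0.05, 83 per arm. The two-proportion formula gives

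n = [1.96·√(2×0.75×0.25) + 0.842·√(0.65×0.35 + 0.85×0.15)]² / 0.20² ≈ 72.4, so 73.

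With the continuity correction, (72.4/4)·[1 + √(1 + 4/(72.4×0.20))]² ≈ 82.1, so 83, as stated. The size needed here is the number randomised: 202 − 18 = 184, or 92 per arm.

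**How one late renal finding is classified.**

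| Category in the safety section | RSDN arm | Control treated as allocated |
|---|---|---|
| RSDN-related | available | cannot apply |
| VT-ablation-related | available | available |
| Unrelated (outside item 13) | available | available |
| Aortography-related | no such category | no such category |

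The RSDN arm has two routes into item 13 and the control arm has one.

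**Illustrative size.** Assumptions, none of them from the documents:

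- the true event rate p is the same in both arms, at 5%, 10% or 15%;
- every RSDN-arm event is called related;
- a share s of control events is called related, with s = 1, 0.75 or 0.5;
- all 92 patients per arm are assessed;
- the arms are compared by a two-sided pooled z-test at 0.05.

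Expected counted events are 92p in the RSDN arm and 92ps in controls. For example, 92 × 0.10 = 9.2 and 9.2 × 0.5 = 4.6. The apparent risk ratio is 1/s: 1.33 at s = 0.75 and 2.0 at s = 0.5, when the true ratio is 1. The chance of p<0.05 comes from summing the exact binomial probabilities over all pairs of counts that reject.

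| p | s | Counted, RSDN v control | Chance of p<0.05 |
|---|---|---|---|
| 5% | 1 | 4.6 v 4.6 | 4.2% |
| 5% | 0.75 | 4.6 v 3.45 | 5.9% |
| 5% | 0.5 | 4.6 v 2.3 | 12.4% |
| 10% | 1 | 9.2 v 9.2 | 5.1% |
| 10% | 0.75 | 9.2 v 6.9 | 9.2% |
| 10% | 0.5 | 9.2 v 4.6 | 24.6% |
| 15% | 1 | 13.8 v 13.8 | 4.9% |
| 15% | 0.75 | 13.8 v 10.35 | 11.6% |
| 15% | 0.5 | 13.8 v 6.9 | 36.8% |

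The rows with s = 1 show the result when every event counts. The error rate is then 4–5%, close to the nominal 5%.

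**The case against.** The strongest reply is that the asymmetry is only a possibility. Item 13 refers to procedures in general and not to RSDN alone. Controls undergo VT ablation, so their haematoma, tamponade, embolism or renal impairment can be attributed to that procedure and counted. Most of item 13's list is ordinary VT-ablation harm shared by both arms. Patients with unsuitable renal arteries are excluded before randomisation, and 6-month imaging is scheduled in both arms, so the underlying data are collected alike. No text says outright that item 13 will be filtered by the categories in the safety section; that link is inferred because no other attribution process is described. All of this stands. It confines the problem mainly to late renal findings, and it means that bias is not shown to occur.

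A reader might infer more than the documents support in four ways.

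- *That the whole safety comparison is limited to related events.* It is not. Items 8, 11, 14, 15 and 16 have no such condition, and death, stroke and MI in item 17 can be read as counting whatever the cause. Item 16 is open-ended and might be used for renal events, but it names none and begins with a word suggesting events not already listed. Item 11 compares laboratory values, not impairment events.
- *That adjudication is known to be unmasked.* The documents are silent. The sentence on the informed operator concerns the person delivering energy, not an adjudicator.
- *That every control renal event is lost.* It can still be assigned to the VT ablation.
- *That the filter would hide a real RSDN harm.* That would require control events to be called related more often than RSDN-arm events, and an RSDN-only category pushes the other way.

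**Conclusion.** The point holds in limited form. Item 13 and the other-serious-event part of item 17 rest on an attribution with no stated masking or criteria. One of its categories is open to only one arm, and none covers the aortography. This can create an apparent RSDN excess in late renal artery stenosis or renal impairment; whether it would do so cannot be told from the plan.

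The size is illustrative only: a false-positive chance of about 6–37% against 4–5%, under the assumed rates and attribution shares. If both arms' events were attributed at the same rate, there would be no bias when the true rates are equal. The primary endpoint is unaffected. This is a worthwhile, inexpensive improvement to two secondary safety endpoints.

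**What to change.** For item 13, compare the randomised arms on all events of each listed type, whatever the attribution. Count from the start of the index procedure through fixed windows, for example 30 days or discharge for acute events, the 6-month imaging for stenosis, and 24 months for renal impairment. The start of the procedure is preferable to randomisation as the origin, because randomisation follows the angiography and acute complications may occur before it. For item 17, count all serious adverse events within its existing 30-day or discharge window. Keep the three-way attribution as a descriptive breakdown beside the comparison.

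The cost is a few sentences of wording. Table 1 and section 9.2.1 already schedule adverse-event review, the 6-month imaging, and BUN/creatinine at 12 and 24 months without restriction by arm, and all adverse events already go to the coordinating centre. The downside is some noise from unrelated background events; the fixed windows limit it.
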